### *Clinical Trial Procedures*

L-DOPA

*Administration.* Prior to pill ingestion, participants would undergo a standardized medical exam (see attached physician screening form) with a study physician to rule out medical and pharmacological contraindications for L-DOPA prescription. Upon passing the medical exam, the study physician would write a prescription to the UW research pharmacy, who maintains the blind, to dispense to our research staff the correct pill. Participants would be randomized to receive either a placebo, 100mg (with 25 mg carbidopa to inhibit peripheral decarboxylase), or 200mg (with 50 mg carbidopa to inhibit peripheral decarboxylase) pill of L-DOPA (see below for randomization and blinding procedures).

The study drug is prepared and maintained by the research pharmacy. Medication is put into two gel capsules, which are identical across the dose ranges of placebo, 100mg and 200mg. Medication kits are prepared separately for the three groups and stored in the locked nurses office of WisPIC along with the study logs of drug administration and allocation for each subject (e.g., subject 001, allocated to group 'blue', provided dose on 2/18/17). There is no washout period required for this study, though participants are required to have been stable on previous medications for at least 4 weeks. Use of MAO-I in past two weeks is exclusionary. As noted above, physician evaluation is performed prior to prescription being written. Participants are assessed for side-effects after 40-min and again 24-hours later.

*Justification and Rationale for L-DOPA Dose Choices.* The dose of 100 mg is consistent with prior studies of L-DOPA on learning as a dose optimizing the inverted U-shaped curve for the dopamine/performance relationship, while the dose of 200 mg is chosen as a suprathreshold dose that establishes the upper bound of the inverted U curve of the dopamine/performance relationship (Monte-Silva, Liebetanz, Grundey, Paulus, & Nitsche 2010; Thirugnanasambandam, Grundey, Paulus, & Nitsche 2011). We chose 200 mg as the suprathreshold dose, as opposed to 300 mg or 500 mg, in order to keep the dose small enough to not inadvertently break the blind (i.e., higher L-DOPA doses are more likely to result in side effects such as dizziness, nausea, fatigue, etc.), and 200 mg has been successfully used in prior learning studies as a suprathreshold dose.

*Double Blind Clinical Trial Methodology.* Neither participants nor research staff would know which pill (placebo, 100 mg L-DOPA, or 200 mg L-DOPA) is given to participants. Instead, for tracking and balanced randomization reasons, groups would be labeled as either "blue", "red", or "yellow", with only a staff member at the UW pharmacy filling the study prescriptions knowing which label received which pill. This pharmacy staff member would have no interaction with the participants.

*Balanced Randomization.* To ensure randomization results in placebo and drug groups balanced on key variables that might affect treatment response, participants would be assigned to treatment conditions through "urn" randomization, which was developed and utilized in previous trials, using Microsoft Access program (Kosten et al. 2003; Oliveto et al. 2011; Poling

**PI: [name].**

et al. 2006). In urn randomization, an algorithm modifies ongoing randomization probabilities based on prior composition of treatment groups, maximizing multivariate equivalence of treatment groups (Wei and Lachin 1988). Thus, urn randomization offers the benefits of balancing allocation of important prognostic variables in treatment groups while still retaining the benefits of random assignment (Stout et al. 1994). Participants will be randomized based on comorbid diagnoses, age, and current medication usage.

*Implementation.* The “urn” randomization will be implemented by a department statistician, who will have no direct contact with the participants and no knowledge of the pill assignment to the group labels and thus has negligible chance of biasing the randomization sequence or implementation.

*Blind Assessors.* The clinical research coordinators performing the assessments will be blind to the treatment conditions; thus minimizing the possibility of systematically biasing the assessment procedures.

#### Study Compensation

Participants will be compensated for their time and participation. They will receive \$60 for the assessment phase, \$70 for Day 1 fMRI, and \$80 for Day 2 fMRI. Participants will also receive \$15 for travel to each of the scheduled appointments, up to 3 visits (\$45). WISPIC and HERI will not be held responsible for replacing lost or stolen checks. Participants may elect to be picked up and transported to the Health Emotions Research Institute through Union Cab at no cost to them.

#### **On-Going Data Collection at the University of Arkansas for Medical Sciences (UAMS).**

This study is additionally enrolling participants at UAMS. Upon completion of data collection, only coded data would be merged across the two sites. That is, participants' data across the sites would be combined into a dataset using only a unique study ID for each subject, and only the site at which the data was collected would be able to link that study ID to the individual participant's PHI. De-identified behavioral data and imaging data would be transferred between sites via SSH on encrypted and firewalled network servers (MRI-APP2.heri.psychiatry.wisc.edu and PRLrocks.ad.uams.edu).

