### Study Population

*Participant recruitment.* Participants will include 105 women aged 21-50. In order to achieve these enrollment goals, up to 260 adults could be recruited and screened for eligibility. Participants will be recruited primarily from the WisPIC outpatient mental health clinic where the PI maintains a clinical practice. We will also recruit through focused community networking with women's shelters and related service organizations and through community-wide general advertisements (e.g., newspaper ads, flyers, etc). We have worked with women's shelters in the past by contacting them to notify them of the study and providing brochures, which then they post in their facility. Interested participants would then contact us to learn more about the study.

*Inclusion/Exclusion Criteria.* Inclusion criteria will be 1) females age 21 – 50 years of age, 2) a current diagnosis of PTSD where the index traumatic event includes physical or sexual assault, 3) English speaking, and 4) medically healthy. Assault exposure will be defined as witnessed or directly experienced exposure to physical or sexual assault (Cisler et al. 2011; Kilpatrick et al. 2000; Kilpatrick et al. 2003; Resnick et al. 1993). To facilitate generalization to real-world populations of women with assault-related PTSD (Kessler et al. 1995; Kessler 2000), current comorbid major depressive disorder or anxiety disorders will not be exclusionary as long as the PTSD diagnosis is primary.

Exclusionary criteria include: 1) internal ferromagnetic objects (such as electronic devices, surgical implants, shrapnel, etc.), 2) major medical disorders (such as cancer), 3) ADHD, 4) psychotic disorders, 5) mental retardation, 6) developmental disorders, 7) active substance use disorders, 8) pregnancy, and 9) glaucoma. Medications will not be exclusionary, as long as the medication has been stable for at least 4 weeks and do not effect neurovascular properties upon which BOLD fMRI capitalizes (e.g., water pills). Acute sedatives / pain killers (e.g., benzodiazepines, vicodin) and prescription stimulants (e.g., Adderall) would not be permitted for 6 hours prior to the scan or for two hours after the scan. Medication prescription use will be modeled as a covariate. See below for detailed exclusion criteria.

Due to safety concerns, participants with these conditions will be ineligible to participate:

- Claustrophobia, or the inability to lie still in a confined space

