### Data analysis.

*Primary Analytic Framework for Fear Extinction Effects.* The overall data analysis framework for Aim 1 fear extinction analyses consists of a 3 (group: placebo vs 100 mg L-DOPA vs 200 mg L-DOPA) x 2 (cue: CS+ vs CS-) x 2 (context: A [learning context] vs B [extinction context]) x 6 (dopamine gene score: 0 [low endogenous dopamine] – 5 [high endogenous dopamine]) mixed design focused on Day 2 fear responding. Preliminary analyses would test for any baseline

differences in fear responding or extinction learning on Day 1 and include these variables as covariates if needed. Analyses would also control for ancestry as well as other demographic or clinical variables should they differ between groups.

*Neural circuit ROI definition and extraction.* The neural circuit indices would be 6 *a priori* regions of interest (ROI) with anatomical coordinates defined from the recent literature (Delgado et al. 2008; Haaker, Gaburro, Sah, Gartmann, Lonsdorf, Meier, Singewald, Pape, Morellini, & Kalisch 2013a; Milad, Wright, Orr, Pitman, Quirk, & Rauch 2007; Phelps, Delgado, Nearing, & LeDoux 2004; Schiller et al. 2008) and include bilateral amygdala, bilateral hippocampus, ventromedial PFC, dorsal anterior cingulate cortex. Following standard preprocessing, first-level analyses conducted for each individual separately would consist of whole-brain GLMs, in which the task design (CS+ vs CS- during Context A vs B) is modeled as boxcar events convolved with a canonical HRF. The task design is regressed onto each voxel's timecourse within a GLM framework and using restricted maximum likelihood to account for serial correlation, resulting in a whole-brain spatial map indicating the degree to which each voxel responds to CS+ vs CS- during Context A vs B. The mean contrast values for CS+ vs CS- as a function of context is then extracted from the voxels within 6 mm spherical ROIs for the six ROIs. These analyses would provide six (for each ROI) indices of activation, calculated separately for each participant, that would be used in multivariate analysis of variance (MANOVA) analyses to define the impact of L-DOPA and dopamine gene score on consolidation of fear extinction learning.

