**Planned Fear Extinction Analyses:** We would conduct three sets of MANOVA analyses, one with the set of Day 2 neural circuit indices (amygdala, dorsal anterior cingulate cortex, caudate) as dependent variables, one with the set of Day 2 physiological indices (SCR, HR, HRV) as dependent variables, and one with the set of Day 2 verbal/self-report indices (anxiety, UCS expectation) as dependent variables. In these analyses, the mixed effects of L-DOPA group, dopamine gene score, cue, context, and the interactions are entered as factors explaining variance in the multivariate combination of the set of dependent variables. Interactions with context would demonstrate the effect of the manipulations on robustness to context renewal effects. Additionally, any factors that differ between groups, such as Day 1 fear responding, age, or comorbid diagnoses, would also be entered as covariates should the balanced "urn" randomization fail. Given the three sets of tests, FDR correction (Benjamini and Hochberg 1995) would be used to control for alpha inflation. If the multivariate analyses reveal significant between-group differences in our measures of neural, psychophysiological and/or verbal/self-report, they would be followed up with simple effect testing to identify the specific conditions and measures driving the larger multivariate effect. We would additionally test for linear and quadratic contrasts for the group comparisons in order to establish dose-dependent learning, and its gating by dopamine gene score, effects on these primary DVs. All analyses would be completed prior to breaking the blind in order to minimize bias.

*Defining dopaminergic resting-state functional connectivity (FC).* Following the prior studies cited above (Haaker, Gaburro, Sah, Gartmann, Lonsdorf, Meier, Singewald, Pape, Morellini, & Kalisch 2013a; Kelly, de, Di, Copland, Reiss, Klein, Castellanos, Milham, & McMahon 2009), we

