*Testing the effect of altered resting-state FC on fear extinction learning consolidation.* Following identification of regions where FC with the DC, VS, and SN/VTA differ as a function of the L-DOPA x gene score interaction, we would then test whether individual differences in FC within these clusters predict subsequent consolidation of fear extinction learning. That is, we would test whether the hypothesized intermediate mechanism (acute dopamine neurotransmission and downstream dopaminergic neural networks) is related to the ultimate mechanism of interest (fear extinction learning). Consolidation of fear extinction learning from Day 1 would again be tested using Day 2 fear expression indices in Context A and Context B (i.e., fear extinction learning recall test) using multimodal assessments (neural circuit indices, psychophysiological, and self-report). GLMs would be used in which the outcome variable is regressed simultaneously onto the FC cluster, L-DOPA group, dopamine gene score, cue, and context. This would be repeated for the separate fear expression indices, with FDR controlling for alpha inflation due to multiple comparisons. These analyses would identify the clusters of voxels whose FC with the VS, DC, and SN/VTA predict enhanced recall on Day 2.

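### Data from two sites are pooled, but no outcome model names site, which leaves the connectivity-to-recall regression open to a false link that balanced arms cannot prevent

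*Combined protocol and SAP*

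**What the plan says.** Section C, in the paragraph on UAMS, states "This study is additionally enrolling participants at UAMS" and then "Upon completion of data collection, only coded data would be merged across the two sites". It adds that "De-identified behavioral data and imaging data would be transferred between sites via SSH". Physiology is not named in that sentence, but the same paragraph combines participants' data from both sites into one dataset.

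Allocation (Section C, Balanced Randomization) uses three urn factors: "Participants will be randomized based on comorbid diagnoses, age, and current medication usage". The text does not say whether the two sites share one urn.

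The covariate rules are spread over several places:
- Section C, Study Population: "Medication prescription use will be modeled as a covariate".
- Section G, Primary Analytic Framework: "Analyses would also control for ancestry as well as other demographic or clinical variables should they differ between groups".
- Section G, Planned Fear Extinction Analyses: "any factors that differ between groups, such as Day 1 fear responding, age, or comorbid diagnoses, would also be entered as covariates", on condition that the urn fails to balance the arms.
- Section G, the group model for FC: covariates enter only if the urn leaves the groups unmatched on demographic or clinical severity variables.
- Section G, the FC-to-recall analysis: "the outcome variable is regressed simultaneously onto the FC cluster, L-DOPA group, dopamine gene score, cue, and context". No covariate clause follows.

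The documents give no number per site, no scanner harmonisation and no cross-site calibration.

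**The concern.** The Day 2 imaging and physiological outcomes and the proposed mediator are instrument readings, and they are collected at two institutions. Separate scanners, recording equipment and staff are a reasonable inference, although the text does not state them.

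The plan's safeguard is to add covariates when the drug arms differ. That suits the randomised comparisons. It does not suit the second step of Aim 2, where FC is the predictor. Arms can be perfectly balanced on site while FC and recall both differ between sites, and FC then predicts recall through site alone. Controlling the false discovery rate deals with the number of tests and does not remove confounding. A false link here would be read as support for the proposed mechanism.

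**Working it through.** **1. The plan's own figure.** Section G states power above .9 for large effects and about .8 for medium-large effects with 35 per group (N = 105). It gives neither alpha nor effect sizes. I assumed a one-way ANOVA with three groups, alpha .05 and a noncentral F with noncentrality f² x 105. Then f = 0.40 gives power 0.960 and f = 0.31 gives 0.807. Both statements reproduce if medium-large means f of about 0.31.

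**2. Where site could enter.** The clause in the Planned Fear Extinction Analyses is open-ended and could admit site, but its trigger is imbalance between arms. The clause for the FC group model is limited to demographic and clinical severity variables. The FC-to-recall model has no clause.

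**3. False FC-recall link, additive shifts.** Let a share p of participants come from one site, and let that site shift FC by d1 and recall by d2, in within-site SDs. With no true link, the induced correlation is

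r = p(1-p)d1d2 / sqrt{[1 + p(1-p)d1²][1 + p(1-p)d2²]}.

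At p = 0.5 and d1 = d2 = 0.8: r = 0.25 x 0.64 / (1 + 0.25 x 0.64) = 0.16 / 1.16 = 0.138. At d1 = d2 = 1.0: r = 0.25 / 1.25 = 0.20.

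I simulated 8,000 trials per setting with N = 105 and one recall value per person. Recall was regressed on FC, two arm indicators and the gene score, and FC was tested at 5%. The shares and shifts are assumptions.

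| Site split | 0.3 SD | 0.5 SD | 0.8 SD | 1.0 SD |
|---|---|---|---|---|
| 50/50 | 5.6% | 9.5% | 28.2% | 54.2% |
| 70/30 | 5.1% | 7.6% | 23.0% | 42.5% |
| 85/15 | 4.9% | 6.2% | 11.2% | 21.6% |

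A repeat at 50/50 gave 5.6%, 8.9%, 29% and 53%. With site in the model the rate is 4.6-5.6% in every setting. If site shifts recall only (0.8 SD, no FC shift), the rate without site stays at about 5%. Both variables must shift.

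**4. Which outcomes this describes.** The regression lists FC as a main effect alongside cue and context. Skin conductance, heart rate, heart rate variability and ratings entered by cue and context can therefore carry an additive site offset into the FC coefficient. The imaging indices are within-person CS+ versus CS- contrasts, so an additive offset cancels. What remains is a gain (scaling) difference or a true site difference in conditioning.

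If the mean contrast is m SDs at one site and the other site scales the signal by g, the outcome shift is m(g-1) / sqrt[(1 + g²)/2]:
- m = 0.2, g = 1.25: 0.05 / 1.132 = 0.04 SD.
- m = 0.5, g = 2.0: 0.5 / 1.581 = 0.32 SD.

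With FC shifts of 0.5-1.0 SD, a 50/50 split and 6,000 runs, the simulated false-positive rate is 4.8-5.7% for m = 0.2 and 5.0-11.1% for m = 0.5, over gains of 1.25 to 2.0.

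**5. Randomised comparisons.** An unmodelled site shift d multiplies the between-person residual variance by 1 + p(1-p)d². At p = 0.5 and d = 0.5 this is 1.0625, so f = 0.31 becomes 0.31 / sqrt(1.0625) = 0.301 and power falls from 0.807 to 0.781. At d = 0.8 power is 0.742. With site in the model it stays at 0.807. An additive offset adds nothing to the error of within-person cue and context interactions.

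**The case against.** Four points on the other side have force.

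- **The imaging outcome.** A reader might take the 28-54% rates to describe the Day 2 neural indices. The documents do not support that, because those indices are within-person contrasts and additive offsets drop out. The applicable figures are the 5-11% in step 4.
- **Routes for site.** A reader might infer that the plan closes off site altogether. It does not: the clause on factors that differ between groups could bring it into the MANOVAs. Day 1 fear responding, if used as a covariate, could also absorb stable site offsets in the same measure. Both are conditional, and neither appears in the FC-to-recall model.
- **Randomised effects.** A reader might infer biased drug comparisons. Randomisation makes them unbiased in expectation, and the cost in between-person tests is modest. The fear-specific effects are interactions with cue, where an additive offset adds no noise.
- **Unknown inputs.** Site shares, equipment and shifts are not given. At 85/15, or with shifts near 0.3 SD, the problem is small.

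It can also be said that physiology and FC come from different devices, so a shift common to both is less direct. That weakens the argument only in part, since the two need not share hardware: it is enough that each differs between sites.

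Control for ancestry partly answers a worry that the gene score differs between recruitment areas. It does nothing about measurement differences.

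**Conclusion.** The gap is real and should be closed. Site is absent from the urn factors and from every listed model, and in the FC-to-recall regression no rule in the plan would bring it in. Arm balance is no defence there.

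The size depends on quantities that the documents do not report. For outcomes that keep an additive offset, the false-positive rate is close to nominal at shifts of about 0.3 SD, and at 0.8 SD it is 11-28% depending on the site split. For the imaging contrasts it is about 5-11% under the gains and mean contrasts examined. All of these rest on a model with no true link, one value per person and N = 105; the additive figures also assume equal shifts in FC and recall. They show what could happen and are not evidence that the two sites differ. The effect on the randomised comparisons is a minor loss of precision.

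**What to change.** Prespecify site as a fixed factor, whether or not the arms differ on it, in this order of importance:

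1. the FC-to-recall regressions;
2. the FC group model;
3. the Day 2 fear extinction models, with site x cue and site x context where cue and context are within-person factors. A site main effect alone cannot remove a gain difference from those effects.

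L-DOPA x site can be an optional sensitivity analysis. The urn need not change for this point, since balancing arms on site does not protect the FC regression.

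The cost is SAP wording, one degree of freedom for site, one each for site x cue and site x context, and two for L-DOPA x site if it is run. The merged file must carry a site code. No participants or procedures are added. The wording should be fixed before the merged data are analysed, because a site term chosen after seeing results would be open to challenge.

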#### **Sharing DNA samples for sequencing and analysis.**

DNA samples will be shared with [name] and the Max Planck Institute for the purposes of sequencing and analysis. Given [name] expertise in PTSD and genetics, she will be a collaborator on subsequent manuscripts describing results from this study.

#### **D. Data and Safety Monitoring**

See separately uploaded Data and Safety Monitoring document.

#### **E. Risks and Benefits**

**PI: [name].**

Potential risks

*Internal metal during MRI scanning.* One potential safety concern is participant internal metal during MRI scanning, which can be dangerous and possibly even lethal. Ferrous metals may exhibit torque or deflection forces while in the presence of the static and gradient magnetic field. Nonferrous metals may absorb radio-frequency (RF) energy during pulse sequences that may cause heating of the metal.

*Possible Peripheral Nerve Stimulation (PNS).* Due the large amount of RF energy emitted during scanning, PNS may occur if certain tissues absorb this energy, manifesting as muscle contractions.

*Possible hearing damage resulting from scanner noise.* Another possible risk involved with scanning is the loud noise of the scanner. While collecting data, the machine may emit sounds at decibel levels high enough to result in hearing damage or loss.

*Electrotactile stimulation during MRI scan.* The risk of electrotactile stimulation includes discomfort, unpleasant sensations, and possibly pain.

*Assessment of mental health and traumatic event exposure.* One potential psychological risk of the proposed study is the possibility that some participants might experience distress or become offended when asked questions pertaining to victimization and mental health history. Nevertheless, there is a specific protocol, should a participant become distressed as a result of participation in this study. This is discussed in detail below.

*Assessment of suicidal ideation.* During the clinical interview in the depression module and the CSSRS, questions regarding suicidal ideation are asked. This may elicit distress from participants; however, there is a specific protocol should a participant report suicidal ideation, intent, or plan, and a protocol to decrease distress, described below.

*Transient distress in relation to the imaging task.* Another potential risk is that the imaging procedure will elicit anxiety/distress. Participants are able to quit the task at any time by indicating to the technician that they wish to do so. Participants have a call button during the imaging session that allows them to indicate to the technician at any time that they wish to stop.

*Personal health information/Loss of confidentiality.* With all research participation, there is a risk that personal information obtained from research participants will be mishandled, and confidentiality may be compromised. With the current vulnerable sample of assaulted women, an associated risk of confidentiality loss is that the abuser might learn of their participation in this study and possibly then retaliate. An additional confidentiality concern is suicidality; that is, if suicidal ideation is observed, it might be clinically indicated to break confidentiality to protect the participants. Additionally, as mandated reporters, if we learn about a situation the participant is involved pertaining to child abuse or elderly abuse, we may have to break confidentiality. Upon IRB approval, we will apply for a certificate of confidentiality.

*Side effects from acute administration of L-DOPA.* It is possible that acute administration of L-dopa can cause transient side effects, such as dizziness, nausea, headaches, and drowsiness.

*Blood draw and genetic testing.* The risks associated with the blood draw itself include discomfort or bruising at the draw site. Because genetic analysis involves information that may uniquely identify participants, there is a risk of genetic information being used to re-identify participants.

*Adequacy of protection against risks.* Procedures to minimize risks identified in the previous section are outlined below.

*Internal metal during MRI scanning.* Participants will be verbally screened several times prior to MRI scanning in order to exclude any participants with internal metal.

*Possible Peripheral Nerve Stimulation (PNS).* All pulse sequences will be conducted with specific absorption rates of <36% in order to reduce the possibility of PNS. Participants will be instructed to notify the study team if they notice any involuntary muscle contractions.

*Possible hearing damage resulting from scanner noise.* All participants will be required to wear ear plugs and noise-canceling headphones to prevent any damage to their hearing.

*Electrotactile stimulation.* Each participant will have the ability (with the assistance of study staff) to calibrate how intense the stimulation is prior to being scanned. Participants will be instructed to select a stimulation level that is “maximally uncomfortable, but in no way painful”. Participants will know exactly what the stimulation will feel like prior to entering the scanner. Additionally, once the participant has been placed in the scanner, prior to beginning the task, they will be asked to confirm their chosen stimulation level. Participants will also be reminded that they may stop the scan at any point if they become uncomfortable.

*Assessment of traumatic event exposure:* Given the vulnerability of the sample, the women will be told that they do not have to answer any questions they do not want to, and that they can withdraw their participant or take a break whenever they want to. Additionally, the trauma assessment interview (from the National Women Survey) is worded with dichotomous questions so that the participant only has to answer yes or no to a series of questions. In our pilot testing with over 70 adult women, we had no adverse events or withdrawals from the study during the trauma assessment. Additionally, if in ascertaining a participant’s current condition, the need for clinical intervention is determined, the appropriate mental health referral will be arranged.

*Procedures for suicidal participants.* Individuals who are actively suicidal, defined as intending to hurt or kill themselves in the acute time frame, will receive immediate crisis counseling services by the UW psychiatrist on call for such emergencies. The treatment response may include hospitalization. These participants will be ineligible for the experimental sessions.

*Transient distress in relation to imaging task.* With regard to potential risks regarding anxiety/distress during imaging, as noted above, the participants are able to quit the tasks at any time using an emergency call button. Participants who wish to terminate early due to distress will be assessed by a clinical psychologist (the PI or the postdoctoral fellow) and appropriate recommendations will be made (e.g., for individual therapy, instruction on coping and affect reduction skills, etc).

*Personal health information/Loss of confidentiality.* Standard practices will be used to protect participant confidentiality and personal health information, including removing identifiers from all data collected, using only numbers to identify participant data, and keeping all data files when not in use in a locked filing cabinet behind a locked office. No names or other identifiers will be used in computerized data files.

Furthermore, some women may participate who are currently in an abusive relationship. In cases such as this, it is sometimes possible that the abuser would become angry and retaliate against the participant for disclosing the abuse. In to protect the participant against possible retaliation from the abuser, we would assess the current safety of the participant with respect to the perpetrator. This clinical assessment would be conducted a female research staff member. Depending on participant need given their unique circumstance, an individualized safety plan would be created for the participant that might include entering therapy, withdrawing participation, entering a women's shelter, contacting the police, etc.

Participants would be notified in the informed consent that confidentiality might be breached in the case of suicidal ideation in order to protect the participant's safety.

*Side effects from acute administration of L-DOPA.* To ensure the participants protection, we escort the participant to a waiting room for monitoring for ~45 minutes after drug administration. We then administer a standardized medication Side Effect Checklist to assess for any side effects that require immediate attention. Upon return to the lab 24 hours later, we re-administer the Side Effect Checklist to assess for any new side effects that require attention prior to beginning the fMRI Day 2 procedures. Participants are additionally given a 24-hour emergency contact number in case of any study-related emergencies.

Side effects of a single low dose of L-DOPA are minimal and might include transient dizziness, nausea, or a general feeling of discomfort. Should these side effects be observed, we would 1) remind participants that these side effects are common and short lasting, 2) tell them they can request to speak with a study's physician if they wish, 3) escort them to the UW ER if they request, or if it is clinically indicated, that they should receive immediate attention. Participants who are unable to continue with the study procedures due to side effects (e.g., not able to complete the resting-state scan 4~5 minutes after pill ingestion) would be removed from the study after following the necessary and indicated clinical procedures (e.g., escorting to ER if necessary, consulting with the study physician, referring to psychiatric treatment as indicated, etc).

**PI:** [name].

*Blood draw and genetic analysis.* To minimize any discomfort during blood draw, only study staff trained to perform blood draw will be allowed to collect the sample from the participant. To protect the identity of research participants and prevent them from being re-identified, all samples sent for analysis will be de-identified. In addition, genetic analysis will be limited to a handful of genes related to the production and movement of dopamine in the brain. This will also minimize the psychological and social risks associated with genetic analysis. Only a few genes will be tested and participants are not re-contacted on the basis of their results.

